Definition of Follow-up Variables

- **Primary Variable:** Change from baseline in GV (MAGE) in mg/dL after 12 weeks of treatment between the DAPA+ MET group versus the MET monotherapy group.
- **Secondary Variables:**
 - Change from baseline (absolute difference) in HbA1c levels (%) after 12 weeks of treatment between the DAPA + MET group versus the MET monotherapy group.
 - Change from baseline (total difference) in insulin levels (μ U/mL) after 12 weeks of treatment between the DAPA + MET group versus the MET monotherapy group.
 - Change from baseline (absolute difference) in oxidative stress measurement (total antioxidant capacity) after 12 weeks of treatment between the DAPA + MET group versus the MET monotherapy group.
 - Change from baseline (total difference) in the measurement of inflammation biomarkers (VCAM-1 and adiponectin) after 12 weeks of treatment between the DAPA + MET group versus the MET monotherapy group.
 - Change from baseline (absolute difference) in body fat quantification after 12 weeks of treatment between the DAPA + MET group versus the MET monotherapy group.
 - Change from baseline (total difference) in the parameters of cardio-metabolic risk factors (weight (kg), total cholesterol (mg/dL), HDL (mg/dL), LDLc (mg/dL), albuminuria (mg/mg creatinine), and blood pressure (mmHg)) after 12 weeks of treatment between the DAPA + MET group versus the MET monotherapy group.

Methods for Data Collection

Electronic Record containing the clinical history collected via telemedicine (Phone call/Videocall, Whatsapp, Teams, Zoom or Google Forms), information gathered at each visit, notes containing patient physical examinations, physical activity questionnaires answered via telemedicine (Phone call/Videocall, Whatsapp, Teams, Zoom or Google Forms), Nutrition notes collected via telemedicine (Phone call/Videocall, Whatsapp, Teams or Zoom), and laboratory results. Patients will only be identified by their initials, date of birth, and the internal protocol folio number.

Monitoring and Auditing Procedures During Study Development

Not applicable

Criteria for Failure and Success

- **Failure:** No decrease in GV in the DAPA + MET group compared to the MET monotherapy group.
- **Success:** A decrease in GV in the DAPA+ MET group compared to the MET monotherapy group.

Sample Size

The sample size was determined using the difference of means formula:

$$n = (Z\alpha / 2 + Z\beta)^2 * 2 * \sigma^2 / d^2,$$

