A reduction in glucose variability from 4.85 to 2.2 was estimated with an expected standard deviation of 2.8 in the MAGE index (values based on the study by R. R. Henry et al., "Effects of Dapagliflozin on 24-Hour Glycemic Control in Patients with Type 2 Diabetes: A Randomized Controlled Trial," *Diabetes Technol. Ther.*, vol. 20, no. 11, pp. 715–724, Nov. 2018.), with an alpha value of 0.05 and a power of 0.80, resulting in a sample size of 88 subjects, with 44 subjects in each treatment group. No adjustments were included in the sample size calculation to estimate the subjects required for the estimated differences in secondary variables.

Description of techniques, devices, and/or instruments to be used (Including special mechanical, electronic, cybernetic equipment)

Continuous glucose monitoring will be performed using the iPro™2 Continuous glucose monitor, from Medtronic®, to determine the MAGE value as follows:

- **Calculation of Mean Amplitude of Glucose Excursion (MAGE):**
 - In the first step, all local maximum/minimum values are determined.
 - The next step is an evaluation of maximum/minimum pairs against the standard deviation (SD).
 - If the difference from minimum to maximum is greater than the SD, this variation from the mean measurement is retained.
 - If the local maximum/minimum is less than 1 SD, it is excluded from further calculations.
 - These channels are retained and summed to achieve the MAGE
- Glycated hemoglobin (HbA1c) will be measured using HPLC (Variant II Turbo, Biorad).
- Insulin levels will be measured with Access-2 equipment (Beckman Coulter, Inc.).
- Oxidative stress will be measured with the BioAssay Systems antioxidant assay kit (DTAC-

100) (QuantiChrom Antioxidant Assay Kit) (BioAssay Systems).

- VCAM-1 will be measured using ELISA kits (Merck Millipore, USA).
- Adiponectin measured using ELISA kits (Merck Millipore, USA).
- Body fat quantification by bioelectrical impedance with the Jawon scale, model⁵ IOI 353 - JMW160.
- Anthropometric variables will be measured using standardized techniques; these include height, weight, waist, and hip circumferences.
- BMI will be calculated using the equation: weight / height² (kg/m²).
- Blood pressure will be measured considering the mean of two determinations after sitting for at least 5 minutes.
- Mean arterial pressure (MAP) will be calculated with the formula: (systolic blood pressure * 0.33) + (diastolic blood pressure * 0.66).

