- Change from baseline (total difference) in the measurement of inflammation biomarkers (VCAM-1 and adiponectin) after 12 weeks of treatment between the DAPA + MET group versus the MET monotherapy group.
- Change from baseline (absolute difference) in body fat quantification after 12 weeks of treatment between the DAPA + MET group versus the MET monotherapy group.
- Change from baseline (total difference) in the parameters of cardio-metabolic risk factors (weight (kg), total cholesterol (mg/dL), HDL (mg/dL), LDLc (mg/dL), albuminuria (mg/mg creatinine), and blood pressure (mmHg)) after 12 weeks of treatment between the DAPA + MET group versus the MET monotherapy group.

Methods to be used to contact patients

Personal contact data such as landline and mobile phone numbers, email address will be obtained via Phone call/Videocall, Whatsapp, Teams, Zoom, or Google Forms. Due to the SARS-CoV-2 pandemic, investigators will conduct home visits and/or collect data and hold medical consultations via Phone call/Videocall, Whatsapp, Teams, Zoom, or Google Forms.

Statistical Analysis (Description of the information processing and presentation plan. Include justification for the statistical tests to be used)

Stratified randomization in both groups to balance patient types and control potential bias. The normality of variables will be analyzed using the Kolmogorov-Smirnov test. According to the distribution of variables, they will be expressed as mean and standard deviation (SD) or median and interquartile range (IQR) for normally or skewed distributed variables, respectively. GV will be determined using the MAGE index. Comparison between the two groups will be evaluated using ANCOVA. A p-value based on two-tailed tests ≤ 0.05 will be considered significant. All analyses will be performed with SPSS 20.0 (Chicago, IL). Patients experiencing an acute stress event during the study will be excluded from the analysis due to the impact on GV.

Justification of sample size (include study power and the p-value considered significant)

The sample size was determined using the difference of means formula:

$$n = (Z\alpha / 2 + Z\beta)^2 * 2 * \sigma^2 / d^2,$$

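### The protocol's success criterion uses only the sign of the difference in GV and is not tied to the planned ANCOVA and two-sided 0.05 test

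*Protocol*

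**What the plan says.** The protocol section Criteria for Failure and Success has two bullets. Success is "A decrease in GV in the DAPA+ MET group compared to the MET monotherapy group". Failure is "No decrease in GV in the DAPA + MET group compared to the MET monotherapy group". Neither bullet mentions a test, p-value, confidence interval, model or size of difference. They refer to GV without naming MAGE, change from baseline or week 12.

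The inferential standard is stated elsewhere in the protocol:

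- The later Statistical Analysis section says "Comparison between the two groups will be evaluated using ANCOVA" and "A p-value based on two-tailed tests ≤ 0.05 will be considered significant".
- The statistical analysis paragraph under General Design compares the changes by ANCOVA, with age, sex, BMI, baseline HbA1c and time since diagnosis as covariates, and uses the same 0.05 threshold. The Summary also names ANCOVA and 0.05.
- The primary variable is "Change from baseline in GV (MAGE) in mg/dL after 12 weeks of treatment between the DAPA+ MET group versus the MET monotherapy group".
- The Sample Size section, directly after the success criteria, uses a formula with Zα/2 and sizes the trial "with an alpha value of 0.05 and a power of 0.80".

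The SAP repeats the sample-size inputs. It contains no success criterion and does not mention ANCOVA. The only tests it names are Student's t and Mann-Whitney, given straight after the baseline comparisons.

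**The concern.** A section headed as the criteria for success and failure is where a reader looks for the rule that decides the primary question. Here that rule depends only on the direction of the difference. The 0.05 rule says when a p-value is called significant. It does not say that success depends on it.

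The two bullets are also complements. A small, non-significant decrease is not an absence of decrease, so on the wording it has to count as success. There is no category for an inconclusive result.

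At stake is which standard a report may cite. The same modest difference could be presented as success under the protocol's stated criterion or as a non-significant primary result under its analysis section. The alpha and power used to size the trial describe only the second of these rules.

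**Working it through.** **Inputs.** From the protocol's Sample Size section: "A reduction in glucose variability from 4.85 to 2.2 was estimated with an expected standard deviation of 2.8 in the MAGE index", so the planned difference is 4.85 − 2.2 = 2.65 and the SD is 2.8; two-sided alpha 0.05; power 0.80; 44 per arm. From the SAP: completers 41 (DAPA+MET) and 39 (MET). I take 2.8 as the SD of the outcome compared between arms and use the normal approximation without covariate adjustment.

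**The plan's own figure.** The success rule carries no stated error rate, so there is none to reproduce. The nearest stated figure is the sample size, "resulting in a sample size of 88 subjects, with 44 subjects in each treatment group". The plan's formula gives n = (1.960 + 0.842)² × 2 × 2.8² / 2.65² ≈ 17.5, so 18 per arm and 36 in total. It does not return 88. That is a separate matter and nothing below depends on it; I use the stated 44 per arm.

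**1. No true effect.** If the estimated difference is distributed symmetrically about zero, P(any decrease) = 0.50, whatever the SD or sample size. For a favourable result at two-sided 0.05 the probability is 0.05 / 2 = 0.025. Simulation of 400,000 trials gave 0.501 (44/44) and 0.499 (41/39) for the first rule, and 0.025 for the second in both cases.

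**2. Where the two rules disagree.** SE = 2.8 × √(1/44 + 1/44) = 0.597. Significance needs an observed difference of at least 1.96 × 0.597 = 1.17, which is 1.17 / 2.8 = 0.42 SD. Observed decreases between 0 and 1.17 meet the success criterion but not the significance standard. The sample-size section gives no unit for its MAGE figures, so 1.17 is in whatever unit those figures are in; 0.42 SD is free of units.

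**3. A truly worse combination (assumed values).** With 44 per arm, P(any decrease) = Φ(−δ/SE):

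- worse by 0.25: Φ(−0.25 / 0.597) = 0.34
- worse by 0.5: Φ(−0.5 / 0.597) = 0.20

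**4. The planned effect.** 2.65 / 2.8 = 0.95 SD. With 41/39 completers, SE = 2.8 × √(1/41 + 1/39) = 0.626 and 2.65 / 0.626 = 4.23.

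- any decrease: Φ(4.23) > 0.999
- significant and favourable: Φ(4.23 − 1.96) = Φ(2.27) = 0.988

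**5. A small effect (0.2 SD, an illustrative assumption; the documents give no such value).** With 41/39, the SE in SD units is 0.224 and 0.2 / 0.224 = 0.894.

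- any decrease: Φ(0.894) = 0.81
- significant and favourable: 1 − Φ(1.96 − 0.894) = 0.14

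| True effect favouring DAPA+MET | Any decrease | Favourable, two-sided p ≤ 0.05 |
|---|---|---|
| 0 | 50% | 2.5% |
| 0.2 SD (assumed, 41/39) | 81% | 14% |
| 0.95 SD (planned, 41/39) | >99.9% | 98.8% |

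**The case against.** The strongest reply is that the protocol, read as a whole, plans a two-sided 0.05 test. ANCOVA with a 0.05 threshold appears in the Summary, under General Design and in the Statistical Analysis section, and the sample size is built on Zα/2. On this view the success bullets are shorthand for the directional hypothesis, and the authors meant a decrease shown by the planned test. The complementary wording of the two bullets proves little, because the same shorthand used twice gives complements under either reading. The documents attach no action to success or failure: there is no interim decision, and the entry for premature suspension of the study is marked not applicable.

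Much of this stands. A reader might infer that the trial has no control of false-positive claims. The documents do not support that, because any claim of significance on MAGE remains subject to the 0.05 test. Nor do they show that the authors rejected the test; the success section is silent on how a decrease is to be established.

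The 50% holds for any sign-only rule and says nothing specific about this drug or sample. The contrast at 0.2 SD depends on a chosen effect and should not be quoted without the planned-effect row beside it.

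What the reply does not supply is a sentence in either document that makes success depend on the test. If significance was intended, stating it costs little. If it was not, the criterion is unsound.

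**Conclusion.** The point holds as a defect in a stated rule. The success criterion, followed as written, depends on sign alone and is linked neither to the planned ANCOVA and two-sided 0.05 standard nor to the alpha used for sizing. With no true effect it is met 50% of the time, against 2.5% for a favourable significant result. At 44 per arm and SD 2.8, the two standards give different answers for observed decreases from 0 to about 1.17 units (0.42 SD).

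The 50% rests only on a symmetric estimate and the literal reading of the bullets. The 1.17 rests on the planning SD applying to the outcome compared, and an adjusted analysis would shift it.

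The practical effect is concentrated where the true effect is absent or small. At the planned 0.95 SD the rules agree in nearly every trial, so it would be wrong to infer that the plan's conclusion is unreliable across the board. The clarification should be made, because the disagreement concerns the primary question and is cheap to remove.

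**What to change.** Replace both bullets in the protocol and carry the same rule into the SAP:

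- *Success:* the between-arm difference in change from baseline in MAGE at week 12, estimated by the ANCOVA with the covariates listed in the General Design analysis paragraph (age, sex, BMI, baseline HbA1c, time since diagnosis), favours DAPA+MET and its two-sided 95% CI excludes zero (p ≤ 0.05).
- *Otherwise:* superiority is not shown. The estimate and its CI are reported, without a claim of no effect.

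The covariates must be named because the later Statistical Analysis section mentions ANCOVA without listing any.

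Record this as a dated clarification, sent to the research committee by the route the protocol gives for deviations from the statistical plan. The SAP was written after recruitment ended and already reports completers and baseline results, so the rule cannot be presented as part of the original plan. The clarification should state whether MAGE results had been seen. Compared with the literal criterion it only makes a claim of success stricter.

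The cost is two sentences and no new data. The downside is that success becomes harder to claim, and a small favourable difference would be reported as inconclusive.

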The guidelines of the American Association of Clinical Endocrinologists recommend the use of combination therapy with MET + another glucose lowering medication when HbA1c at diagnosis is >7.5 and $\leq 9\%$, and in patients with HbA1c $>9\%$ without classic symptoms of diabetes; dual or triple therapy can also be initiated [23]. In a study of 16 T2D patients, dapagliflozin 5 mg showed statistically significant improvement in body composition (fat mass) from week 8 [49]. In another study of 40 hypertensive patients treated with dapagliflozin vs hydrochlorothiazide, an impact on blood vessel vasodilation was found after 4 weeks of dapagliflozin treatment [50]. The effect of administration of dapagliflozin decreased glycemic excursions, reduced GV, and prevented atherosclerosis damage in preclinical studies [45]. In a case report of a patient with MODY, administration of gliclazide with dapagliflozin improved GV [46].

Henry et al. [37], using CGM, determined GV in patients with uncontrolled T2D (HbA1c 7.5% to 10.5%) who were previously treated with Metformin >1500 mg/day (50%) or insulin > 30 units/day (50%), to whom dapagliflozin or placebo was additionally administered. A decrease of 18.2 mg/dL in average glucose with CGM and a decrease of 15.3 mg/dL in MAGE were reported. Based on this study, the sample size calculation was performed.

9. Problem Definition

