A reduction in glucose variability from 4.85 to 2.2 was estimated with an expected standard deviation of 2.8 in the MAGE index, with an alpha value of 0.05 and a power of 0.80, resulting in a sample size of 88 subjects, with 44 subjects in each treatment group. No adjustments were included in the sample size calculation to estimate the number of subjects required for the

estimated differences in secondary variables.

Recruitment potential (number of subjects intended to recruit)

It is estimated that approximately 15% of the subjects who start the project and enter the pre-randomization period will not meet the criteria for the treatment period. Therefore, it is estimated that approximately 102 subjects will be assessed.

If multicenter, include the global and local sample number

Not applicable

Procedures for reporting deviations from the original statistical plan

A letter will be sent to the research committee for approval.

Possible discomforts resulting from the study

Frequency of follow-up visits, blood sample collection.

Potential risks

Those inherent to blood sampling.

Methods for detecting anticipated risks

Patients will be asked to report any side effects 24 hours a day. Patients will be able to contact the participating medical staff at any time.

Safety measures for timely diagnosis and prevention of risks

Patients reporting a side effect will be scheduled for evaluation.

Procedures to follow to resolve risks if they occur

Depending on the case, treatment for the complication or side effect will be provided, either with an outpatient prescription or the patient will be referred to the emergency department for assessment and treatment. Medical expense insurance will be available to cover treatment costs for patients associated with adverse effects secondary to the use of study medications.

Expected direct benefits

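### The stated sample size inputs give about 18 patients per group, not 44, and the planning effect does not match the 15.3 mg/dL MAGE effect cited as its source, so the 80% power claim is wrong

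*Protocol*

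**What the plan says.** The protocol gives the calculation under Methods (SAMPLE SIZE), in the Sample Size section and under Justification of sample size. The SAP repeats it in its opening paragraph. The inputs and the result are the same each time.

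- **Method:** "The sample size was determined using the difference of means formula". In the two full protocol statements and the SAP the formula is printed as n = (Zα/2 + Zβ)² × 2 × σ² / d².
- **Effect and spread:** "A reduction in glucose variability from 4.85 to 2.2 was estimated with an expected standard deviation of 2.8 in the MAGE index". No unit is attached to 4.85, 2.2 or 2.8. The Sample Size section attributes them to the cited dapagliflozin continuous glucose monitoring (CGM) trial.
- **Error rates:** "with an alpha value of 0.05 and a power of 0.80". The Statistical Analysis section specifies two-tailed tests.
- **Result:** "resulting in a sample size of 88 subjects, with 44 subjects in each treatment group".

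The Background describes the same cited trial and says: "a decrease of 15.3 mg/dL in MAGE were reported. Based on this study, the sample size calculation was performed". The primary variable, under Definition of Follow-up Variables and again under Outcomes and Variables, is "Change from baseline in GV (MAGE) in mg/dL after 12 weeks of treatment".

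**The concern.** A sample size statement should let the reader put the inputs into the formula and get the printed n. Here the implied standardised difference is 2.65 / 2.8 = 0.95, a large effect that needs far fewer than 44 per group at 80% power. The planning difference also does not resemble the effect reported elsewhere in the protocol from the trial it is said to come from.

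This is the only power statement for the primary endpoint, and it stands in both documents. If the trial finds no difference in MAGE, a reader will take that as a null result from a study with 80% power for a defined effect. As written, the documents do not identify any effect for which 88 patients give 80% power.

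**Working it through.** **Inputs.** d = 4.85 − 2.2 = 2.65; SD = 2.8; two-sided alpha 0.05 (Z = 1.960); power 0.80 (Z = 0.842); 1:1 allocation. All are from the protocol sections named above.

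**Attempt to reproduce 44 per group.**

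n = (1.960 + 0.842)² × 2 × 2.8² / 2.65² = 7.849 × 15.68 / 7.0225 = 17.5, so 18 per group and 36 in total.

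With the t distribution, 18 per group gives 78.8% power and 19 gives 81.0%, so 19 per group and 38 in total. The stated 44 is about 2.4 times the computed 18, which is too far apart for rounding.

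**Could an unstated step bridge the gap?** Each line changes one thing in the formula.

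| Variant | n per group |
|---|---|
| One-sided test | 14 |
| 90% power | 24 |
| 95% power | 30 |
| 99% power | 42 |
| SD multiplied by √2 (change score, no correlation) | 36 |
| 18 inflated for 10% to 30% dropout | 20 to 26 |
| d = 2.2 instead of 2.65 | 26 |
| d not squared | 47 |

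None gives 44 at the stated 80% power. To reach 44 one would need d of about 1.67 with SD 2.8, or an SD of about 4.44 with d = 2.65, or a dropout allowance of 1 − 18/44 = 59%. None of these is stated. The 15% under Recruitment potential is loss before randomisation and is added on top of 88 (88 × 1.15 = 101.2, so 102).

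**Power that 44 per group gives on the stated inputs.** 99.2% (t distribution). With the 41 and 39 completers reported in the SAP it is 98.7%.

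**Difference that 44 per group detects with 80% power.** 0.60 SD, which is 1.69 when the SD is 2.8. With 41 and 39 it is 0.63 SD.

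**Planning effect against the cited effect.** Using 18 mg/dL per mmol/L:

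- If 2.65 is in mg/dL: 2.65 / 15.3 = 0.17, about one sixth of the cited effect.
- If 2.65 is in mmol/L: 2.65 × 18 = 47.7 mg/dL, and 47.7 / 15.3 = 3.1 times the cited effect.

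**Power for 15.3 mg/dL.** The documents give no SD for this effect, so the SDs below are assumptions (two-sided 0.05, t distribution).

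| Assumed SD of MAGE change (mg/dL) | Power, 44 per group | Power, 41 and 39 |
|---|---|---|
| 15 | 99.7% | 99.5% |
| 20 | 94% | 92% |
| 25 | 81% | 77% |
| 30 | 66% | 61% |
| 40 | 43% | 39% |
| 50.4 (2.8 read as mmol/L, × 18) | 29% | 27% |

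At 44 per group, power is 80% when the SD is about 25 mg/dL (15.3 / 0.604 = 25.3). In the last row, 80% power would need about 172 per group.

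**The case against.** Four points can be made on the other side.

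- **Direction.** On the stated inputs the trial is larger than it needs to be, so the arithmetic error cannot by itself have cost power. This is correct and limits what the error shows.
- **No SD for 15.3 mg/dL.** Low power for the cited effect is possible, not shown. No section uses mmol/L, so the 29% rests on an assumed unit, and an SD of 20 mg/dL or less gives 94% or more. Read literally in mg/dL, an SD of 2.8 would put power for 15.3 mg/dL at essentially 100%, though so small an SD is implausible. This stands, and it is why power must be shown over a range.
- **The two effects may not be the same quantity.** The Background does not say whether 15.3 mg/dL is a fall within one arm or a difference between arms, and the sample size text does not say which of these the move from 4.85 to 2.2 represents. This stands too, but the formula used compares two groups and the documents say the calculation rests on that study. An undefined d is part of the fault.
- **Consequence.** The SAP reports recruitment closed, with 88 randomised and 80 completers. A correction changes no patient, test or estimate, and a null result should be read mainly from its confidence interval. That is fair, but it does not make a wrong power statement acceptable in both governing documents.

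None of this restores the printed result: no stated step leads from 18 to 44.

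**Conclusion.** The concern holds. The printed formula and inputs give 18 per group (19 by t) against the stated 44, and 44 per group gives about 99% power on those inputs, not 80%. This rests only on figures in the documents and is certain.

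The planning difference of 2.65 agrees with the cited 15.3 mg/dL in neither mg/dL nor mmol/L. That comparison treats both as the same kind of difference, which the documents do not establish.

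Whether the trial has adequate power for 15.3 mg/dL cannot be settled from the documents. At 44 per group it has at least 80% power if the SD of MAGE change is about 25 mg/dL or less, and less than 80% if the SD is larger. Because this is the only power claim for the primary endpoint, it must be corrected.

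**What to change.** Keep 88 patients and correct the text in all four places: protocol Methods (SAMPLE SIZE), Sample Size and Justification of sample size, and the SAP's opening paragraph.

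1. Delete the claim that a difference of 2.65 with SD 2.8 requires 88 patients.
2. State what the design provides: 44 per group gives 80% power, at two-sided 0.05, for a between-group difference of about 0.60 SD in MAGE change. This follows from n alone and does not justify the choice of effect, so items 3 and 4 are needed with it.
3. State the assumed SD of MAGE change in mg/dL and its source. Say what d represents, and reconcile it with the 15.3 mg/dL in the Background.
4. Give the power for 15.3 mg/dL over a range of SDs that includes values below and above 25 mg/dL.

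The cost is wording in two documents, with no extra patients and no change to the analysis. The restated power for the cited effect may turn out less favourable than 80%. Since the SAP already reports enrolment and follow-up as complete, the new text should be marked as a correction made afterwards and not presented as the planning calculation.
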